6.7.4.2. Duration of Response

The DoR time is defined only for responders (patients with a BOR of CR or PR). It is measured from the date of first evidence of CR or PR to the date of objective progression or the date of death due to any cause, whichever is earlier. It is calculated as date of progression or death – date of first response evaluation of CR or PR + 1. The DoR will be censored according to the same rules as PFS, with the addition of the following rule: if a patient begins post discontinuation therapy, DoR will be censored on the day of the last response evaluation prior to the initiation of post discontinuation therapy.

A KM analysis of DoR will be performed to estimate the DoR curve for each arm. Point estimates and CIs for DoR quartiles and DoR rates will be calculated every 6 months for the first 18 months.

6.7.5. Sensitivity Analyses

6.7.5.1. Progression-Free Survival

Sensitivity analyses will be undertaken for calculation of the primary endpoint in order to evaluate the robustness of the analysis. The following sensitivity analyses will be performed for PFS:

Progression-Free Survival Sensitivity Analysis 1 (censoring for receiving subsequent systemic anticancer therapy): if a patient is initiated on another anticancer therapy prior to objective progression, including any postdiscontinuation treatment systemic therapy, radiotherapy, or surgical intervention, PFS will be censored at the date of the last complete objective progression-free disease assessment before initiation of the new therapy.

Progression-Free Survival Sensitivity Analysis 2 (nonobjective progression as a PFS event): if a patient is discontinued from study treatment due to investigator determined non-objective progression (for example, symptomatic deterioration), then the patient's PFS time will be calculated using the date of non-objective progression as the progression date.

Progression-Free Survival Sensitivity Analysis 3 (forward-dating progressions at unscheduled assessments): if a patient has objective progression at an unscheduled disease assessment, then the PFS time for that patient will be forward-dated to the next scheduled disease assessment.

Progression-Free Survival Sensitivity Analysis 4: Progression-free survival will also be analyzed after adjusting for selected prognostic factors. Potential prognostic factors include the stratification factors and other factors as outlined in Section 6.12. The HR for treatment effect will be estimated using a multivariate Cox proportional hazard model constructed by selecting variables among all the potential variables, using stepwise selection method with entry p-value 0.05 and exit p-value 0.01. The treatment factor will be kept out of the model throughout the covariate selection process and only added into the final model.

In addition, a PFS analysis based on independent central review data will be conducted. Details can be found in the Central Review SAP.

6.7.5.2. Overall Survival

One sensitivity analysis on OS is planned. Overall survival time for this analysis defined as the time from the date of study enrollment to the date of death due to study disease. Survival time will be censored on the date the patient was last known to be alive for patients who have no reported event. For patients that have died due to reasons not disease related, survival time will be censored at the date of death.

Additional sensitivity analyses may be conducted to evaluate the impact of follow-up systemic therapy with another CDK4/6 inhibitor on OS. Survival times may be censored at the time of follow-up systemic therapy, and the time-dependent Cox model and inverse probability of treatment weighting method to adjust for the impact of follow-up therapies and time-dependent factors on survival might be used (Robins et al. 2000).

6.8. Health Outcomes/Quality-of-Life Analyses

6.8.1. Instruments

Patient-reported outcomes are measured through paper versions of the following:

- the EORTC QLQ-C30
- the EORTC QLQ-BR23
- the EQ 5D 5L.

6.8.2. Quality of Life

Data from the EORTC QLQ-C30 instrument will be scored as described by Aaronson and colleagues (Aaronson et al. 1993). The EORTC QLQ-BR23 data will be scored as described by the EORTC scoring manual (Fayers et al. 2001). The key quality of life items and domains for comparative statistical analysis will be the pain item (item 9), physical functioning domain, and emotional functioning domain from the EORTC-QLQ-C30 questionnaire.

A mixed effects, repeated measures model will be applied to compare treatment arms by cycle with respect to each instrument. The model will include baseline score as a covariate and an unstructured covariance matrix will be utilized. For each instrument, the analysis will include all cycles for which at least 25% of patients in each arm have an assessment.

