9.4. Selection and Timing of Doses

Blinded study drug will be taken orally every $12 (\pm 2)$ hours on Days 1 through 28 of a 28-day cycle, for a total of 56 doses per cycle. During all cycles, blinded study drug should be taken at approximately the same times each day. If a patient misses or vomits a blinded study drug dose, that dose should be omitted.

Anastrozole or letrozole will be administered orally every 24 hours (±2) on Days 1 through 28 of a 28-day cycle for a total of 28 doses per cycle. For PK and electrocardiogram (ECG) purposes, anastrozole or letrozole should be administered at the same time as (or up to 20 minutes after) the morning dose of blinded study drug through Cycle 4, Day 1. Subsequently, the interval between administration of blinded study drug and anastrozole or letrozole may be adjusted based on the judgment of the investigator. If a patient misses or vomits an anastrozole or letrozole dose, that dose should be omitted.

A cycle is defined as an interval of 28 days plus any subsequent delay prior to start of the next cycle. A delay in the start of a cycle due to holidays, weekends, bad weather, or other unforeseen circumstances will be permitted up to 7 days and not counted as a protocol deviation). For each 28-day cycle, a total of 56 doses of blinded study drug will be dispensed. In exceptional cases, for planned delays (including but not limited to vacation or holidays), additional study treatment may be dispensed.

A patient may continue to receive study treatment until she meets 1 or more of the specified reasons for discontinuation (as described in Section 7.3.1).

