Tumor Assessment	Radiological imaging according to RECIST (CT scan/MRI)	Section 10.1.1 Attachment 5			X			X	Performed locally. For patients with locoregionally recurrent breast cancer not amenable to curative treatment, MRI scan of the breast is performed, if applicable, in addition to other scans. Imaging studies (Breast MRI and CT scan or MRI of the chest, abdomen, and pelvis) will be repeated on Day 21 to Day 28 of every second cycle beginning with Cycle 2 and continuing through Cycle 18 (inclusive), on Day 21 to Day 28 of every third cycle after Cycle 18, and within 14 days of clinical progression. The same method of imaging used at baseline should be used for each subsequent assessment.
	Bone Scintigraphy	Section 10.1.1 Attachment 5						X	Performed locally. Repeat for all patients on Day 21 to Day 28 of every sixth cycle beginning with Cycle 6. In addition, bone scans should be repeated even if a complete response is identified in target disease or progression in bone is suspected. Importantly, RECIST v1.1 emphasizes that bone scintigraphy is not adequate to measure bone lesions; however, bone scintigraphy can be used to confirm the presence or disappearance of bone lesions.
	X-ray, CT scan with bone windows, or MRI	Section 10.1.1 Attachment 5			X			X	Performed locally for patients with bone lesions identified by bone scintigraphy at baseline. Repeat on Day 21 to Day 28 of every second cycle beginning with Cycle 2 and continuing through Cycle 18 (inclusive), on Day 21 to Day 28 of every third cycle after Cycle 18, and within 14 days of clinical progression. For patients with new lesions identified by post-baseline bone scintigraphy, targeted assessment by X-ray, CT scan with bone windows, or MRI will be performed to confirm findings.

Protocol I3Y-MC-JPBM				Study Treat	ment Period		
During Trea Schedule	tment Study	Cycle / Visit	1	2	3	4-X	
		Approximate Visit Duration (days)	28	28	28	28	
		Relative day within a cycle	1	1 21- 28	1	1 21-28	
Procedure Category	Procedure	Protocol Reference					Comments
Health Outcomes	EORTC QLQ-C30, EORTC QLQ-BR23, EQ-5D 5L	Section 10.2	Х		X	X	Patients complete prior to extensive interaction with site staff. On Cycle 1 Day 1, questionnaires must be administered prior to the first dose of study treatment. Questionnaires should be administered on Cycle1 Day 1, and then Day 1 of every second cycle beginning with Cycle 3 through Cycle 19, and on Day 1 of every third cycle after Cycle 19.

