- Modification to the definition for baseline value of an efficacy assessment to include an assessment prior to first dose if no assessment prior to the date of randomization is available.
- Clarification to the definition of a treatment emergent adverse event.
- Inclusion of list of consolidated MedDRA preferred terms used for adverse event reporting.

Statistical Analysis Plan Version 4 was approved after unblinded safety analyses by the DMC but prior to unblinding of the sponsor and prior to the first interim analysis for efficacy. The overall changes and rationale for the changes incorporated in Version 4 are as follows:

- The OS analysis after 236 OS events was replaced by analyses after 189 and 252 OS events.
- A statement was added to specify the key quality of life items and domains for comparative statistical analysis to meet registration requirements.
- The list of consolidated MedDRA preferred terms was updated in Appendix 1 following medical review of observed adverse events.

Statistical Analysis Plan Version 5 was approved after unblinded safety analyses by the DMC but prior to unblinding of the sponsor and prior to the first interim analysis for efficacy. Version 5 updates the gated analysis of OS to split alpha between the ITT population and the population of patients with visceral disease at baseline.

4. Study Objectives

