6.8.3. Health State Utility

The EQ-5D 5L data will be scored as described by van Hout et al. (van Hout et al. 2012). The index score is calculated from a set of item weights to derive a score of 0 to 1, with 1 representing the best health status. Geographic-specific weights will be used as appropriate and when available. The Visual Analog Scale (VAS) is scored from 0 (*worst imaginable health state*) through 100 (*best imaginable health state*) to represent the patient's self-report for each day. The EQ-5D 5L responses for each item will be summarized by frequency and corresponding percentages. Descriptive statistics for the index and VAS will be calculated by arm and cycle. Psychometric analyses, including calculation of reliability coefficients (Cronbach's alpha), will also be performed.

For both the index score and VAS, a mixed effects, repeated measures model will be applied to compare treatment arms by cycle. The model will include baseline score as a covariate and an unstructured covariance matrix will be utilized. The analysis will include all cycles for which at least 25% of patients in each arm have an assessment.

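### SAP 6.8.2 and 6.8.3 compare quality of life cycle by cycle with no prespecified summary contrast, leaving up to about 10 unadjusted comparisons per measure and no single answer to the secondary objective

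*SAP*

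**What the plan says.** SAP 6.8.2 states that the key measures for comparison "will be the pain item (item 9), physical functioning domain, and emotional functioning domain from the EORTC-QLQ-C30 questionnaire". The Revision History (SAP section 3) explains why Version 4 introduced them: "A statement was added to specify the key quality of life items and domains for comparative statistical analysis to meet registration requirements". The analysis is then: "A mixed effects, repeated measures model will be applied to compare treatment arms by cycle with respect to each instrument". Baseline score is a covariate and the covariance is unstructured. The cycles analysed follow from a completion rule: "For each instrument, the analysis will include all cycles for which at least 25% of patients in each arm have an assessment". SAP 6.8.3 repeats the arrangement for the EQ-5D index and VAS: "a mixed effects, repeated measures model will be applied to compare treatment arms by cycle".

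The visits come from Protocol Attachment 1. After the Cycle 1 baseline, forms are given on "Day 1 of every second cycle beginning with Cycle 3 through Cycle 19, and on Day 1 of every third cycle after Cycle 19".

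The protocol does not supply the missing contrast. Its synopsis foresees descriptive analysis and, where suitable, a repeated measures comparison. Section 12.2.11 adds a descriptive maximum change from baseline and leaves the rest to the SAP. Section 12.2.11.3 says only that the EQ-5D index and VAS go into a repeated measures model. The alpha-controlled graph in SAP 6.7.3.1 contains PFS and then OS; quality of life is not in it.

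**The concern.** Change in symptom burden is a listed secondary objective on which the arms are to be compared (Protocol 6.2, SAP 4.2). The SAP narrows the outcomes to three key measures but does not say what the treatment effect on each one is. A model that compares arms by cycle returns one estimate per qualifying cycle. If some favour abemaciclib and others do not, the plan gives no basis for saying whether quality of life differed.

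Each by-cycle comparison defaults to the general level (two-sided 0.05 in Protocol 12.2.1), with no adjustment across cycles or across the three measures. How many comparisons there are depends on observed completion through the 25% rule. The late ones rest on few control patients. At stake is how a supportive result, prepared with registration in mind, can be read.

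**Working it through.** The documents state no quality-of-life power, error rate or between-visit correlation, so there is no plan figure to reproduce. The check counts the comparisons and then bounds the error rate.

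**Inputs from the documents.** Cycle length: "A cycle is defined as an interval of 28 days plus any subsequent delay prior to start of the next cycle" (Protocol 9.4). Month = 365/12 days (SAP 6.1.2). Control median PFS 10 months, exponential, hazard ratio 0.67, 450 patients randomized 2:1 (SAP 5.2). Abemaciclib median = 10/0.67 = 14.9 months.

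**Assumptions.** Patients leave treatment at the planned PFS rate. The 25% in the cycle rule is taken as a share of all randomized patients in the arm, because the SAP does not define the denominator.

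**Step 1: cycles that qualify with full follow-up and complete forms.** Time at Day 1 of cycle c is t = (c - 1) x 28/(365/12) months. The share still on treatment is 0.5^(t/median).

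| Cycle | t (months) | Control | Abemaciclib |
|---|---|---|---|
| 3 | 1.8 | 88.0% | 91.8% |
| 11 | 9.2 | 52.8% | 65.2% |
| 15 | 12.9 | 40.9% | 55.0% |
| 19 | 16.6 | 31.7% | 46.3% |
| 22 | 19.3 | 26.2% | 40.7% |
| 25 | 22.1 | 21.6% | 35.8% |

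Cycles 3, 5, ..., 19 (nine visits) and Cycle 22 pass, and Cycle 25 fails in the control arm. That gives 10 comparisons per scale.

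**Step 2: how fragile the 10 is.**
- With 5% missing forms, Cycle 22 drops out: 0.262 x 0.95 = 0.249.
- Cycle 19 drops out if completion is below 0.25/0.317 = 79%.
- With 80-95% completion and 0-20% per year other dropout (assumed), 7 to 9 cycles qualify.
- With a data cut at 240 PFS events and uniform accrual over an assumed 12 months, the cut falls at about 20.6 months. Cycle 15: (20.6 - 12.9)/12 x 0.409 = 0.26, passes. Cycle 17: (20.6 - 14.7)/12 x 0.360 = 0.18, fails. So 7 cycles qualify. The same holds for accrual of 8 or 18 months.
- At 189 events (cut at about 16.5 months for 12-month accrual), Cycle 11 passes at (16.5 - 9.2)/12 x 0.528 = 0.32. Cycle 13 fails at (16.5 - 11.0)/12 x 0.465 = 0.21. So 5 cycles qualify.
- In the other direction, a control median of 12 or 14.7 months would give 11 or 13 cycles with full follow-up.

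**Step 3: chance of at least one false difference per measure.** For k independent two-sided 5% tests it is 1 - 0.95^k: 40.1% for k = 10, 30.2% for k = 7, 22.6% for k = 5. For correlated test statistics, the probability that any |Z| exceeds 1.96 was found from 400,000 multivariate-normal draws.

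| Equal correlation (assumed) | k = 5 | k = 7 | k = 10 |
|---|---|---|---|
| 0.3 | 21% | 27% | 35% |
| 0.5 | 18% | 23% | 29% |
| 0.7 | 15% | 18% | 21% |
| 0.9 | 10% | 11% | 13% |

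For k = 10, autoregressive correlation of 0.5 to 0.9 gives 36% to 19%. Equal correlation of 0.5 to 0.8, weakened for dropout between visits, gives 32% to 23%. Counting only one-sided 0.025 results in favour of abemaciclib, k = 10 gives 1 - 0.975^10 = 22% if independent, 14% at correlation 0.5 and 11% at 0.7.

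**Step 4: late precision.** Without covariate adjustment, the standard error of a by-cycle difference is SD x sqrt(1/n1 + 1/n2).
- Cycle 3: n = 300 x 0.918 = 275 and 150 x 0.880 = 132, giving 0.11 SD.
- Cycle 19: n = 300 x 0.463 = 139 and 150 x 0.317 = 48, giving 0.17 SD.

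**Step 5: after the fix.** One contrast per measure carries 5%. Three unadjusted contrasts give 1 - 0.95^3 = 14.3% if independent, or at most 5% with Holm.

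**The case against.** The strongest reply is that nothing confirmatory rests on these comparisons. Quality of life is outside the testing graph, no claim or decision depends on any cycle's p-value, and the protocol synopsis treats symptom burden as largely descriptive. The reference to registration requirements is unexplained and states no claim. The SAP contains other unadjusted repeated comparisons: PFS rates every 4 months to 24 months (6.7.2.3.1), OS rates at 1, 2 and 3 years (6.7.3.4), and ORR, DCR and CBR (6.7.4.1). This stands as a limit on importance. It does not remove the gap, because PFS and OS each have a log-rank test as their single answer and the quality-of-life measures have none.

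The second reply is that the size depends on assumptions. That also stands. A reader might take 10 tests, or one particular error rate, as a property of the plan. The documents do not support that: 10 needs complete forms and full follow-up, and any error rate needs a correlation that they do not give. A combined rate for the three measures needs a between-measure correlation as well; for 10 cycles it is about 44-70% under assumed values of 0.3-0.7 within and 0.4-0.6 between measures.

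The third reply is that averaging is one choice among several. A fixed cycle would also serve, an average can hide an early effect that later reverses, and equal weights give imprecise late cycles full weight. The 25% rule still decides which cycles enter. These are fair. Any one prespecified contrast would close the main gap; the average uses all the included visits.

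**Conclusion.** The point holds as a cheap improvement to a supportive analysis. The gap itself is textual and needs no simulation: even if by-cycle results were perfectly correlated, a list of estimates is not one prespecified treatment effect.

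The size is up to about 10 unadjusted comparisons per measure under the SAP's 10-month control median, and likely 5 to 9 in practice. The chance of at least one false two-sided difference per measure is about 13-40% for 10 comparisons (equal correlation of 0.9 down to independence; about 29% at 0.5) and about 18-30% for 7 (0.7 down to independence). It is roughly half that for differences favouring abemaciclib alone. These ranges rest on assumed correlations, exponential dropout at the planned PFS rates, and the all-randomized reading of the 25% rule.

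Two stronger inferences fail. The trial's type I error for PFS and OS is untouched, because quality of life takes no part in that graph. Nor does the plan permit choosing a favourable cycle to report: the model yields every included cycle. The fault is that the plan does not say which result answers the objective.

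**What to change.** In SAP 6.8.2 and 6.8.3, state that the comparative analysis for each scale is one contrast from the model already planned: the treatment difference averaged with equal weights over the included post-baseline cycles. Present by-cycle differences with confidence intervals as descriptive.

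In 6.8.2, also state whether the three key QLQ-C30 measures are Holm-adjusted or reported as nominal.

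The cost is two or three sentences and one contrast statement per scale, with no new data, visits or model. The downside is that an effect confined to a few cycles is shown descriptively and not tested. The set of cycles averaged would still depend on observed completion through the 25% rule, so the report should list them.

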4.2. Secondary Objectives

The secondary objectives of the study are to compare the combination treatment of abemaciclib and NSAI therapy versus placebo plus NSAI therapy with respect to the following:

- overall survival (OS)
- overall survival rate at 1, 2, and 3 years;
- objective response rate (clinical response + partial response [ORR = CR + PR]);
- duration of response (DoR) for CR + PR;
- disease control rate (DCR = CR + PR + stable disease [SD]);
- clinical benefit rate (CBR = CR + PR + SD \geq 6 months);
- the safety and tolerability;
- change in symptom burden from baseline using the European Organization for Research and Treatment of Cancer Quality of Life Questionnaire Core 30 (EORTC QLQ-C30), EORTC QLQ-BR23 (breast) questionnaire, and health status scores from the EuroQoL 5-Dimension 5 Level (EQ-5D 5L);
- the pharmacokinetics (PK) of abemaciclib, its metabolites, and NSAI therapy.

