5.1. Summary of Study Design

Study I3Y-MC-JPBM (JPBM) is a multicenter, randomized, double-blind, placebo-controlled, Phase 3 study evaluating treatment of abemaciclib with NSAI or placebo with NSAI in postmenopausal women with hormone receptor-positive (HR+), HER2- locoregionally recurrent (not amenable to curative therapy) or metastatic breast cancer who have not received prior systemic therapy in this disease setting.

Figure JPBM.5.1 illustrates the study design.

Abbreviations: HER2- = human epidermal growth factor receptor 2-negative; HR+ = hormone receptor-positive; N = number; NSAI = nonsteroidal aromatase inhibitor; PD = progressive disease; R = randomized.

Figure JPBM.5.1. Illustration of study design.

Approximately 450 patients will be randomized 2:1 between the 2 arms:

- Experimental Arm A: abemaciclib 150 mg orally every 12 hours on Days 1 to 28 plus either anastrozole 1 mg or letrozole 2.5 mg once daily of a 28-day cycle
- Control (Placebo) Arm B: placebo orally every 12 hours on Days 1 to 28 plus either anastrozole 1 mg or letrozole 2.5 mg once daily of a 28-day cycle.

Patients will be randomized using the following stratification factors: nature of disease (visceral metastases versus bone-only metastases versus other) and prior (neo)adjuvant endocrine therapy (aromatase inhibitor therapy versus other versus no prior endocrine therapy). The presence of visceral metastases refers to lung, liver, pleural, peritoneal, or adrenal gland involvement at the time of randomization. Prior (neo)adjuvant endocrine therapy refers to aromatase inhibitor

therapy (e.g., anastrozole, exemestane and letrozole) versus other (e.g., tamoxifen and fulvestrant) versus no prior endocrine therapy.

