5.2. Determination of Sample Size

The study will enroll approximately 450 patients in 2:1 randomization.

A 2-look group-sequential design of the primary endpoint of investigator-assessed PFS will be used to accommodate an event-driven plan for the interim and final PFS analyses (see Section 6.7.2 for details). There is 1 planned interim analysis and 1 final analysis for PFS in this study. The interim analysis is planned to take place after approximately 189 investigator-assessed PFS events have occurred. The primary PFS analysis will be performed after 240 PFS events have occurred. The cumulative 1-sided type I error rate of .025 will be maintained using the method described in Section 6.7.2.2. Assuming a hazard ratio (HR) of 0.67, this sample size yields more than 80% statistical power to detect superiority of the abemaciclib plus NSAI arm over the placebo plus NSAI arm with the use of a 1-sided log-rank test and a type I error of 0.025. If the true median PFS for the placebo plus NSAI arm is 10 months, then the HR of 0.67 amounts to an approximately 5-month (50%) improvement in median PFS for the abemaciclib plus NSAI arm under an additional assumption of exponential survival distribution.

6. A Priori Statistical Methods

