6.7.1.2. Stratification Factors

The stratification factors for the analysis of primary and secondary analyses are:

- nature of disease (visceral metastases vs bone only metastases vs other)
- prior (neo)adjuvant endocrine therapy (aromatase inhibitor vs other vs none).

The stratification factors are captured in the IWRS and on electronic clinical (case) report forms (eCRFs). Unless otherwise specified, all stratified analyses will be based on the stratification factors per IWRS. A cross tabulation of the frequency of each level of each stratification factor per IWRS and eCRF will be produced.

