6.7.4. Other Secondary Endpoints

6.7.4.1. Objective Response Rate, Disease Control Rate, and Clinical Benefit Rate

Objective response rate (ORR), disease control rate (DCR), and clinical benefit rate (CBR) are summary measures of best overall response (BOR) as defined by RECIST v1.1. BOR is derived from time point responses. All time point responses observed while on study treatment and during the short term follow up period (but before the initiation of post discontinuation therapy) will be included in the derivation. The one exception includes patients who receive surgery and/or radiotherapy for locally advanced breast cancer. For these patients, only those time point responses occurring prior to surgery/radiotherapy will be included in the derivation.

Each patient's BOR will be categorized as CR, PR, SD, progressive disease (PD), or not evaluable (NE). For patients with bone-only nonmeasurable disease (see Section 6.4.2), BOR will be limited to CR, SD, PD, and NE. Patients with SD will be further classified as SD \geq 6 months or SD <6 months. Stable disease \geq 6 months includes all patients with a best response of SD and a PFS time of \geq 6 months. A BOR of CR or PR will not require confirmation.

Objective response rate is the proportion of patients with a BOR of CR or PR. Clinical benefit rate is the proportion of patients with a BOR of CR or PR, or SD \geq 6 months. Disease control rate is the proportion of patients with a BOR of CR, PR, or SD. Patients with bone-only nonmeasurable disease cannot have a best response of PR, thus ORR will be reported for both the ITT population and the subset of patients with measurable disease.

For each of these rates, point estimates and confidence intervals (using the normal approximation to the binomial) will be calculated by treatment arm. Stratified tests comparing these rates between treatment arms will be conducted using a Cochran-Mantel-Haenszel (CMH) test.

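### The quality-of-life and EQ-5D mixed models do not name the randomization strata, so their reported standard errors may be slightly too wide

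*SAP*

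**What the plan says.** **The design.** SAP 5.1 states: "Patients will be randomized using the following stratification factors: nature of disease (visceral metastases versus bone-only metastases versus other) and prior (neo)adjuvant endocrine therapy". Each factor has three levels. SAP 5.2 adds: "The study will enroll approximately 450 patients in 2:1 randomization".

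**The quality-of-life models.** Change in symptom burden and health status is a secondary objective (SAP 4.2: "change in symptom burden from baseline using the European Organization for Research and Treatment of Cancer Quality of Life Questionnaire Core 30", with the BR23 and EQ-5D 5L). SAP 6.8.2 picks out the C30 pain item and the physical and emotional functioning domains for comparative analysis. The revision history for Version 4 ties that choice to registration requirements. The model compares arms by cycle, and its stated content is: "The model will include baseline score as a covariate and an unstructured covariance matrix will be utilized". For EQ-5D, SAP 6.8.3 says: "For both the index score and VAS, a mixed effects, repeated measures model will be applied to compare treatment arms by cycle", with the same baseline-score and covariance sentence. Baseline score is the only covariate named in either section.

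**Strata elsewhere in the SAP.** SAP 6.7.1.2, under the Efficacy Analyses heading, begins its list of the two factors with "The stratification factors for the analysis of primary and secondary analyses are". It also fixes their source: "Unless otherwise specified, all stratified analyses will be based on the stratification factors per IWRS". The sections on the log-rank tests (6.7.2.2, 6.7.3.3) and Cox models (6.7.2.3.1, 6.7.3.4) each state their own stratification. So does the response-rate section, 6.7.4.1: "Stratified tests comparing these rates between treatment arms will be conducted using a Cochran-Mantel-Haenszel (CMH) test". Not every comparison is treated this way: the normal-approximation comparisons of PFS and OS rates carry no stratification statement.

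**The concern.** An analysis should normally reflect the factors used in the randomization. Stratifying makes the arms more alike than chance would, which reduces the sampling variability of the treatment difference. A model without the strata still counts the between-stratum variation as residual noise, so its reported standard error does not show the balance that the design bought. Protocol 8.2 gives reduced bias and improved power as the purpose of stratifying, and the quality-of-life models as written do not collect the second benefit.

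Nature of disease could plausibly bear on pain and physical function, two of the three C30 measures singled out for comparison.

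Missing data are a second reason. Under the Protocol's Attachment 1, questionnaires are given on treatment and at the 30-day visit, but not in long-term follow-up. Progression is a reason to stop treatment (Protocol 7.3.1). SAP 6.2 imputes nothing except dates, and 6.8.2 analyses cycles with as few as 25% of patients per arm. The mixed model therefore has to handle dropout alone, through a missing-at-random assumption that is easier to defend when predictors of dropout are in the model.

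**Working it through.** The documents give no sample size, power, standard deviation or effect size for quality of life or EQ-5D, so there is no planned figure to reproduce.

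**Inputs.**
- From the documents: about 450 patients at 2:1, so 300 and 150; two factors with three levels each; two-sided 0.05 (the default in Protocol 12.2.1), critical value 1.96.
- Assumed: R², the share of outcome variance left after baseline score and treatment that the strata explain, at 2%, 5% and 10%. An 80% power starting point is also assumed.

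**Step 1. Reported against true standard error.** Let S be the standard error reported without strata and r = √(1 − R²). With stratified randomization and full follow-up, the true standard error is about rS whether or not the strata are fitted. The reported value is therefore too large by a factor 1/r.

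**Step 2. Type I error without strata.** The test compares the estimate with 1.96S, but the estimate varies with standard error rS. Two-sided error is 2[1 − Φ(1.96/r)].

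**Step 3. Power.** Without strata, power is Φ((δ − 1.96S)/(rS)). Setting this to 80% gives δ = S(1.96 + 0.8416r). With strata, the test uses rS, so power is Φ(δ/(rS) − 1.96) = Φ(1.96/r + 0.8416 − 1.96).

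| Assumed R² | r | 1/r | 1.96/r | Type I error without strata | Power with strata (80% without) |
|---|---|---|---|---|---|
| 0% | 1.000 | 1.000 | 1.960 | 5.0% | 80.0% |
| 2% | 0.990 | 1.010 | 1.980 | 4.8% | 80.6% |
| 5% | 0.975 | 1.026 | 2.011 | 4.4% | 81.4% |
| 10% | 0.949 | 1.054 | 2.066 | 3.9% | 82.8% |

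**Step 4. Simulation with full follow-up.** A single-visit analysis of covariance stood in for the repeated measures model: 4,000 runs, N = 450, stratified 2:1 randomization, no true effect, outcome SD 1, residual SD 0.8 after baseline. Block size 6 and the stratum shares were assumed. By formula, S = 0.8 × √(1/300 + 1/150) = 0.080, and rS at R² = 10% is 0.949 × 0.080 = 0.0759. The simulation at R² = 10% gave:
- empirical standard error 0.0760 without strata and 0.0759 with;
- reported standard error 0.0801 without and 0.0760 with;
- type I error 4.0% without and 5.0% with.

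At R² = 2%, type I error was 4.9% without and 5.0% with.

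**Step 5. Simulation with dropout.** With about 60% missing, related to visceral disease and arm (assumed pattern), and R² = 10%, the mean estimate under no effect was 0.009 without strata and 0.001 with. The Monte Carlo error is about 0.13/√4,000 = 0.002, so the first figure is a real but small bias. Empirical standard errors were 0.131 without and 0.128 with.

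**Step 6. Cost.** Main effects use 2 × (3 − 1) = 4 degrees of freedom. At the smallest admissible cycle, 25% of 300 and 150 is about 75 and 38, or 113 patients, which still leaves room for four terms.

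**The case against.** The case against has four parts.

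1. **The text is silent; it does not exclude the strata.** The sentence in 6.8.2 says that baseline score is included. It does not say that nothing else is, and it leaves out treatment, cycle and their interaction, which a comparison by cycle needs. SAP 6.7.1.2 could be read as already covering secondary analyses, and so quality of life. This stands in part. A reader might infer that the SAP contradicts its own rule. The documents do not support that, because 6.7.1.2 sits under efficacy and quality of life has its own section. Where the SAP uses strata it says so locally, so the plain reading of 6.8.2 and 6.8.3 is that the models leave them out.

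2. **No precision is lost in the estimate.** This stands for full follow-up (Step 4). A reader might infer that the trial throws away precision and calculate power as Φ((1.96 + 0.8416)/r − 1.96), which gives 80.8%, 82.0% and 84.0%. That formula assumes that adding the strata shrinks the true standard error, as it would under unstratified randomization. Here the design has already delivered that gain, and Step 3 gives the smaller figures.

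3. **The size is assumed.** This stands. Disease site may act largely through the baseline score, which is already in the model, and then the remaining R² is close to zero.

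4. **No controlled conclusion depends on it.** This also stands. The testing graph in SAP 6.7.3 contains only PFS and OS, and the Protocol synopsis treats symptom burden descriptively, with a repeated measures model where appropriate.

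**Conclusion.** The point holds and is small. As written, the two models do not carry the randomization factors, and no reason is given. The consequence is a slightly conservative analysis: reported standard errors about 1%, 3% or 5% too large, and power of 80.6%, 81.4% or 82.8% in place of 80%, at assumed R² of 2%, 5% or 10%. At R² near zero there is no effect.

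These figures rest on the assumed R² range, full follow-up, and a single-visit model standing in for the repeated measures model. With dropout related to the strata there is a further modest benefit in bias and precision, shown only under the assumed pattern in Step 5.

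A reader might infer that the quality-of-life tests are invalid or that the main results are weakened. Neither follows. Without strata the error rate falls below the nominal level, the PFS and gated OS log-rank tests are stratified, and quality of life carries no allocated alpha.

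**What to change.** In SAP 6.8.2 and 6.8.3, write out the fixed effects: baseline score, treatment, cycle, treatment-by-cycle, nature of disease and prior (neo)adjuvant endocrine therapy, the last two taken from the IWRS as 6.7.1.2 already does for stratified analyses. Settle the wording before the sponsor is unblinded.

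The cost is one sentence in each section, four degrees of freedom and no new data.
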